Journey of Transformation Curriculum for Native American Adolescents (JOT)

NCT05274217

[name]

Statistical Analysis Plan

IRB Approved 03-16-2021

Statistical Design and Power

This study will evaluate the following primary outcomes: (1) alcohol, tobacco, and other drugs (ATOD; intentions to use, overall use, susceptibility, refusal self-efficacy) and (2) sexual and reproductive health (sexual activity, sexual self-efficacy, safer sex intentions). An intent-to-treat approach will be used to estimate the magnitude and statistical significance of intervention effects at immediate post-intervention. Each outcome will be evaluated in a separate generalized linear mixed model to evaluate the effect of CHJOT curriculum on intervention outcomes. Continuous outcomes will be modeled using a Gaussian link function for normally distributed data and binary outcomes using a logit link for Bernoulli-distributed data. The following equation represents the basic model for the outcomes: $Outcome_{tij} = b_0 + b_1 Intervention_i + b_2 Time + b_3 (Intervention_{ij} \times Time_{tij}) + u_{0i} + r_{0ij} + e_{tij}$, where t indexes assessment, i indexes individual, and j indexes classroom. The last three terms on the right side of the model equation represent the variability between classrooms (u_{0i}), between individuals within classroom (r_{0ij}), and residual error (e_{tij}), respectively. The statistical test of the CHJOT curriculum will be the Intervention by Time interaction, which will evaluate whether recipients of the intervention curriculum improved more or decreased less from pre- to 2-month post-intervention compared with waitlist control.

To estimate the necessary sample size for our Longitudinal Mediation Model. We assume 80% power to detect a small intervention effect of $d = 0.22$ (standardized mean effect) of CJT (immediate intervention) vs. Waitlist control in pre-intervention to 3 month post-intervention outcome change. We base our power analysis on a repeated measures ANOVA design evaluating the Intervention by Time interaction in the primary outcome analysis, assuming a Type I error rate of 5%. Assuming a moderate temporal stability ($r = .25$) of the outcome measures, which is reasonable given the short interval between assessments, post-baseline data from 255 participants will be necessary to detect an intervention effect equivalent to a Cohen's d as low as 0.20, which would accommodate a 10% reduction in the observed intervention effect due to potential early exposure of control participants to the intervention (i.e., contamination effects). We anticipate a modest attrition rate of 15%, as the intervention will be offered in a required class in a boarding school indicating an analytic sample of 216 participants. Thus, our planned recruitment of 255 participants will provide a sufficient sample to detect targeted intervention effect, after accounting for attrition.

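### The SAP tests seven primary outcomes in separate models, with no multiplicity control and no rule for turning seven results into one conclusion

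*SAP*

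**What the plan says.** The first paragraph of the SAP's Statistical Design and Power section places two groups of measures under the label of primary outcomes. The substance-use group is "intentions to use, overall use, susceptibility, refusal self-efficacy", which is four measures. The sexual and reproductive health group is "sexual activity, sexual self-efficacy, safer sex intentions", which is three.

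On analysis it says "Each outcome will be evaluated in a separate generalized linear mixed model", and "The statistical test of the CHJOT curriculum will be the Intervention by Time interaction". The stated aim covers both the size and the statistical significance of the effects. That makes seven primary models and seven primary tests.

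The second paragraph sets the sample size. It says "We assume 80% power to detect a small intervention effect of" d = 0.22, for a single interaction test, "assuming a Type I error rate of 5" per cent. That is the only error rate in either document. It is not said to apply to each outcome test or to the family of tests, and sidedness is not given.

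Neither the SAP nor the protocol contains a multiplicity adjustment, a testing order, a domain score, a global test, a lead outcome, or a statement of how many outcomes must succeed.

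**The concern.** With seven primary tests and no rule for reading them together, the basis for a claim of efficacy can be settled after the results are known. Nothing in the plan stops a single p-value below 0.05 out of seven from being reported as success on a primary outcome.

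The documents attach consequences to success. Protocol section 1.8 says the data will underpin later large-scale efficacy studies and that a successful project would matter to other Native schools. Section 5.10 makes release of the training manuals and curriculum depend on efficacy having been shown. Neither section says what pattern across the seven outcomes would count as showing it.

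Seven may also be a minimum. Protocol section 1.5 separates number of partners from condomless intercourse and adds delayed sexual initiation. Section 5.4 measures alcohol, cigarettes and vaping, and no rule combines them into one overall-use variable.

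**Working it through.** **Inputs.** From the SAP: 4 + 3 = 7 primary outcomes; type I error 5%; d = 0.22, or 0.20 after a 10% contamination loss; temporal correlation r = 0.25; 255 recruited, 15% attrition, 216 analysed. Assumed here: each test is two-sided at 5%, and any one significant result is treated as a success. The correlation between outcomes is not given, so a range is shown. The SAP's r = 0.25 is the stability of one measure over time and cannot be used for it.

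**The plan's own sample size.** The attrition step reproduces: 255 × 0.85 = 216.75. The 255 does not. For a repeated measures ANOVA interaction with two groups and two times, λ = f² × N × 2 / (1 − r), taking f = d/2 as an assumption. This needs N = 297 for d = 0.20 and N = 246 for d = 0.22 at 80% power. The multiplicity point does not depend on that mismatch.

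**Chance of at least one false significant result, no true effect.**

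- Independent, either direction: 1 − 0.95^7 = 0.302.
- Independent, favouring the curriculum only: 1 − 0.975^7 = 0.162.
- Correlated: simulation of seven equally correlated normal test statistics, 1,000,000 draws.

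| Correlation between test statistics | Either direction | Favouring the curriculum only |
|---|---|---|
| 0 | 30.2% | 16.2% |
| 0.2 | 28.8% | 14.7% |
| 0.5 | 23.0% | 11.5% |
| 0.7 | 17.9% | 8.9% |
| 0.8 | 14.9% | 7.4% |

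**What adjustment costs.** Holm compares the smallest p-value with 0.05/7 = 0.0071, the next with 0.05/6 = 0.0083, and so on up to 0.05. At the first step, with 216 analysed:

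- d = 0.20: λ = 0.10² × 216 × 2 / 0.75 = 5.76. Power is 66.6% at 0.05 and 37.8% at 0.0071.
- d = 0.22: λ = 0.11² × 216 × 2 / 0.75 = 6.97. Power is 74.8% at 0.05 and 47.1% at 0.0071.
- Restoring 80% for a given outcome at 0.0071 would need 472 analysed (d = 0.20) or 391 (d = 0.22).

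These levels depend on f = d/2. If d is instead the difference in mean change in SD units of the raw score, a change-score calculation at d = 0.20 with 216 analysed gives 22.4% at 0.05 and 6.8% at 0.0071.

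**Power for at least one adjusted claim.** If all seven outcomes truly shift by d = 0.20 (f = d/2, 216 analysed), simulation gives about 78% to 79% at correlation 0.5, depending on whether a t or normal critical value is used. At correlation 0.8 it is about 62%. The single unadjusted test has 67%.

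**The case against.** Several points on the other side stand.

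- A reader might infer that the plan makes any one significant result a success, and so that the trial's error rate is 23% to 30%. The documents do not support that. The SAP gives no success rule of any kind, and the figures measure one permissive reading of the gap. The lower end also assumes a correlation of 0.5. Intentions, susceptibility and refusal efficacy are related constructs, so higher correlations and lower rates are possible.
- A reader might also infer that a 5% guarantee is being broken. The SAP never claims 5% family-wise control. Its 5% is the per-test rate in a power calculation, and applying it to each outcome test is an inference.
- For a false claim of benefit, the relevant rate counts one direction only, which roughly halves the figures.
- Protocol section 1.5 aims at preliminary efficacy and section 1.8 calls the trial phase 2, with larger studies to follow. Missed signals have a cost too, and how strictly to control error at this stage is a judgement.

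One objection carries less weight. The SAP numbers two domains, and two independent tests would give only 1 − 0.95² = 9.75%. But no domain score is defined and each outcome has its own model, so seven is the natural count.

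**Conclusion.** The gap is real: seven declared primary outcomes, seven tests, no multiplicity control and no decision rule, in a trial sized for one test. The size is conditional. With two-sided 5% tests and any single significant result presented as success, the chance of a false significant primary result runs from about 30% (independent) through 23% (correlation 0.5) to 15% to 18% (0.7 to 0.8). Limited to results favouring the curriculum, it is about 16% if independent and 12% at 0.5. Even at 0.8, the either-direction figure is about three times 5%.

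The preliminary purpose lowers the stakes. It does not remove the need for a rule, because the SAP calls all seven primary, promises significance tests, and the protocol ties later decisions to demonstrated efficacy. This should be corrected before results are seen. It does not invalidate the design.

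**What to change.** Add a rule to the SAP. Keep all seven models with their estimates, confidence intervals and unadjusted p-values. Base any claim of primary efficacy on Holm-adjusted p-values across the seven outcomes at 5% overall. Describe outcomes significant only before adjustment as preliminary signals for the later large-scale studies. State that tests are two-sided if that is intended, and define overall use and sexual activity as one variable each so that the count stays at seven.

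This needs a few sentences and no extra data. The SAP should state the loss of power at the strictest step shown above and note that later Holm steps are less strict. The loss for the trial's overall conclusion is smaller if the effect is spread across outcomes, and larger if only one outcome moves.

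If that loss is unacceptable, one lead outcome per domain could be named in advance and tested at 0.025. On the same calculation this needs 359 analysed at d = 0.20 or 298 at d = 0.22 for 80% power, still above 216.

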5 PROCEDURES

5.1 Study procedures. Using lay language, provide a complete description of the study procedures, including the sequence, intervention or manipulation (if any), drug dosing information (if any), blood volumes and frequency of draws (if any), use of records, time required, and setting/location. If it is available: Upload a study flow sheet or table to **Zipline**.

For studies comparing standards of care: It is important to accurately identify the research procedures. See UW IRB [POLICY Risks of Harm from Standard Care](#) and the draft guidance from the federal Office of Human Research Protections, ["Guidance on Disclosing Reasonably Foreseeable Risks in Research Evaluating Standards of Care"](#); October 20, 2014.

Information about pediatric blood volume and frequency of draws that would qualify for expedited review can be found in this [reference table](#) on the Seattle Children's IRB website.

Research activities will be conducted by UW and [REDACTED] staff and begin the first week of class: for the waitlist group – the group starting in spring, they will only take the baseline assessment in the Fall and begin the intervention steps as described below beginning in the spring. Thus they receive one more assessment than students in the immediate intervention group (fall). UW staff will be on hand to answer any questions at each assessment time point. Please note the follow-up assessment are about 10 minutes shorter as we will not be any lifetime behaviors questions

Week 1. Take a 30-40 minute online baseline assessment.

UW and [REDACTED] staff will set up laptops or students will have their own laptop. Students will be emailed a link, they will sign onto their laptops and link into the survey. The student

will enter their response directly into the questionnaire. Students will be given a Native designed t-shirt and water bottle.

Weeks 1-3. Meet with a mentor who will help students set goals to improve their health goals around sexual health and/or reduce or avoid alcohol, tobacco, or other substance use. They may meet with the mentor one more time within this time period (for a total of two meetings). The masters-level mentors are provided by the [REDACTED] and trained by a certified motivational interviewer trainer hired by UW.

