Week 1 – 8 (month 1-2). As part of their health class, attend 16 health sessions related to healthy behaviors and developing behavioral skills for health promotion. Sessions will be led by [REDACTED] staff. The study session curriculum will emphasize youth as leaders, storytellers, and environmental stewards and highlight the importance of connecting to their own tribal traditions.

Week 9- 16 (month 3-4). **Optional** additional activity. Participate in once a month activity (booster sessions).

The activities will help build youth leadership skills and include drum making, and storytelling vest making that incorporate their own cultural symbols, and up to two outdoor activity field trips. The field trips are to a places of cultural significance near the school and involve a 30-45 minute hike. Activities are between 1-2 hours and delivered by the [REDACTED] staff after school or on weekends.

Week 9 (Month 3) take the online post intervention assessment via a link sent to their email address by the UW staff

Week 16 (month 4) **Optional** additional activity. Meet with their mentor for a booster MI session to revise their vows for health and community leadership.

Week 9 -24 (month 3 - 6). **Optional** additional activity. Attend a digital storytelling training and up to three monthly planning sessions to prepare for digital storytelling leadership premiere night. Training and planning sessions are 1-2 hours long and held after school. Students will be asked to create a digital story about a health promotion activity of their choice for their community. Some examples may be an increase in cultural activities through participating in traditional games, an increase in promoting healthy lifestyle by planting a traditional garden or a medicine garden base on their own tribal plants. These activities are delivered by the UW and [REDACTED] staff.

Week 24 (Month 6) take the online follow-up assessment via a link sent to their email address by the UW staff

Week 25 (Month 6): **Optional** additional activity. Attend a leadership premiere night, present their digital stories and/or share a story that they have learned about health promotion and celebrate their health leadership journey.

Help prepare the leadership night traditional feast and giveaway that will honor their community culture and values.

Month 12: Take the online follow-up assessment via a link sent to their email address by the UW staff

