At the orientation meeting, a study package will be handed to each youth. The package will include Native items such as sage or lavender, a writing pad and pen and pencil with a Native design and study phone number, two copies of the assent form (one for them to sign and the other to keep as their copy), and the study flyer. UW and [REDACTED] staff will inform the students about the research project, highlighting that it is

completely voluntary and then review the assent form and ask for questions. At the end of the meeting, students will be instructed to write their names on the assent form and indicate if they are interested in participating in the project (Yes/No) or would like more information. Students who are interested in participating will also be asked to fill out a contact information sheet, which asks for their name(s), birth date, preferred pronouns, email address, phone number, and space to provide any additional contact information (ex., social media). If they would like more information, they will be asked to provide contact information (similar to that of those who have assented) and a UW staff person will contact them. They will be informed that they may also reach out to the UW or [REDACTED] staff at any time before the first day of class (within the two weeks) if they have any additional questions about participation.

Students will hand in one signed copy of the assent form when they exit the room.

UW or [REDACTED] staff will then follow-up with students that indicated they are interested in participating and welcome them to the program and asked if they have any additional questions. They will also follow-up with students who request additional information.

For students that have indicated they are interested, they will be randomly assigned to a class offering the intervention sessions. Some classes will start the intervention curriculum in the Fall, others in the Spring. Students that indicated they are not interested they will be assigned to a class that is not participating in the intervention curriculum. This is easily done as there are multiple classes for each grade.

Students may choose to drop out of the research program by notifying research staff by email and reassignment to a health class will be provided. As standard practice, students periodically change class assignments so this would not seem out of the norm.

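### The classroom term in the primary model drops out of the Intervention-by-Time test, so the test runs above its 5% level if classes differ in change

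*SAP*

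**What the plan says.** The SAP (Statistical Design and Power) introduces its equation with "The following equation represents the basic model for the outcomes". The equation has fixed effects for intervention, time and their product, plus three random terms. The SAP describes these as follows: "The last three terms on the right side of the model equation represent the variability between classrooms", then between students within a classroom, then residual error. On the test it says: "The statistical test of the CHJOT curriculum will be the Intervention by Time interaction". On sample size it says: "We base our power analysis on a repeated measures ANOVA design evaluating the Intervention by Time interaction". That paragraph has no clustering input.

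Protocol Section 1.6 specifies individual-level randomisation. Section 7.2 says of interested students that "they will be randomly assigned to a class offering the intervention sessions" and continues: "Some classes will start the intervention curriculum in the Fall, others in the Spring". Each class therefore belongs to one arm. Section 5.1 describes group delivery: "As part of their health class, attend 16 health sessions related to healthy behaviors". It puts the baseline survey in week 1 and says of the waitlist group that "they will only take the baseline assessment in the Fall". Neither document mentions a classroom-by-time term, cluster-robust standard errors or a small-sample correction. Neither gives a class count, a class size or an ICC.

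**The concern.** The SAP recognises that classmates may resemble each other and puts a classroom term in the model. As written, that term absorbs only differences between classes that are the same before and after the intervention. Randomisation makes such differences small at baseline, and the difference-in-change test removes them anyway.

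The differences that matter arise between the week 1 survey and the post-test, from a shared facilitator, shared peers and shared sessions. They appear as class differences in change, and the model has no term for them. Because classes are nested in arm, this variation feeds directly into the treatment comparison.

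Every primary outcome is analysed with this one model. The stakes are a false-positive rate above the stated 5%, intervals that are too narrow, and less power than claimed, in a trial meant to inform larger studies.

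**Working it through.** **Inputs from the SAP.** 216 analysed, pre/post correlation r = .25, 5% level (two-sided assumed), 15% attrition, and the random terms above.

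**Assumptions, not in the documents.** Unit variance at both assessments; equal arms; classes of 12, 18 or 27 analysed students (18, 12 or 8 classes); class variance arising only at post-test; ICC of 0 to .10 as a share of post-test variance.

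**The plan's own figures.** The 5% level reproduces when the ICC is 0 (4.9% to 5.2% in simulation). The sample size of 255 at d = 0.20 does not reproduce: the usual repeated measures formula with f = d/2 gives 297 (246 at d = 0.22). That is a separate matter.

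**Step 1: cancellation.** For one student,

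post − pre = b2 + b3 × Intervention + (e_post − e_pre).

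Both intercepts are gone. The variance of change is 2(1 − .25) = 1.5, so

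SE(b3) = √[1.5 × (1/108 + 1/108)] = 0.1667.

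Generalised least squares under the SAP covariance gives 0.1667 for every classroom-intercept variance from 0 to 0.5. With 15% of post-tests missing it moves only from 0.17336 to 0.17339. In four REML fits to data simulated with class differences in change, the SAP model's SE equalled the plain change-score SE (0.1440, 0.1567, 0.1644, 0.1545). Adding classroom-by-time raised it to 0.2398, 0.2234, 0.3236 and 0.1807.

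**Step 2: design effect (DE).** A post-test ICC becomes ICC/1.5 on the change scale. With m analysed students per class:

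- both arms clustered: DE = 1 + (m − 1) × ICC/1.5
- immediate arm only (the average of that DE and 1): DE = 1 + (m − 1) × ICC/3

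At m = 18 and ICC .05:

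- both arms: 1 + 17 × .05/1.5 = 1.567, effective sample 216/1.567 = 138
- one arm: 1 + 17 × .05/3 = 1.283, effective sample 216/1.283 = 168

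**Step 3: type I error.** The approximation is 2[1 − Φ(1.96/√DE)]. At m = 18 and ICC .05 it gives 11.7% (both arms) and 8.4% (one arm). Null simulation of the change-score test, 20,000 trials per cell, in percent:

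| Classes × size | Clustered arms | ICC 0 | .01 | .02 | .05 | .10 |
|---|---|---|---|---|---|---|
| 18 × 12 | both | 5.2 | 5.9 | 7.1 | 9.3 | 13.6 |
| 12 × 18 | both | 5.0 | 6.6 | 7.9 | 11.7 | 18.2 |
| 8 × 27 | both | 5.1 | 6.7 | 9.1 | 15.5 | 23.2 |
| 18 × 12 | immediate only | 5.0 | 5.2 | 6.1 | 6.9 | 9.8 |
| 12 × 18 | immediate only | 4.9 | 5.9 | 6.7 | 8.1 | 12.2 |
| 8 × 27 | immediate only | 4.9 | 6.1 | 6.6 | 10.0 | 15.1 |

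The ICC scale matters. An ICC of .05 defined on change rather than on the post-test gives 15.1% for 12 classes with both arms clustered.

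**Step 4: attrition.** The SAP mixed model was fitted by REML with a Wald z test: 12 classes, 254 enrolled, 15% of post-tests missing at random, 2,000 trials. It gave 5.1%, 7.8%, 13.8% and 19.1% at ICC 0, .02, .05 and .10 (both arms), and 9.5% and 11.4% at .05 and .10 (immediate arm only).

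**Step 5: binary outcomes.** Under the logit link the cancellation is not an algebraic identity, but a constant intercept still cannot represent class differences in change. With an assumed 30% prevalence and 12 classes of 18, the likelihood-ratio test of b3 gave 3.9%, 11.6% and 18.6% at ICC 0, .05 and .10 (both arms) and 9.9% at .05 (immediate arm only). This rests on 700 trials, with Monte Carlo error of about 0.7 to 1.5 points, and is less firm than the Gaussian results.

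**Step 6: the remedy.** A t-test on class-mean changes, with degrees of freedom equal to classes minus 2, stayed between 4.7% and 5.6% in every Gaussian cell.

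**The case against.** The strongest reply is that the defect is conditional and its size unknown. With no ICC or class count in the documents, every percentage above is assumption-driven, and if class variance in change is zero the test is correct. That stands, and it is why the result is given as a range. It does not justify a plan that relies on an unstated zero when the SAP itself expects classrooms to vary.

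Second, the protocol can be read to mean that waitlist students are not taught together before their comparison measurement, which makes the one-arm rows the more relevant ones. This has force. But Section 7.2 has students assigned to classes that start in Fall or Spring, and neither document says where waitlist students sit in the meantime. Both cases therefore stay open.

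Third, classes of 27 analysed students would need about 32 enrolled at 15% attrition (27/.85). Annual cohorts and changes of class also point to smaller or weaker clusters. The top of the range is therefore less likely. Individual mentor meetings could cut either way, since mentor caseloads are not given.

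Fourth, the SAP calls its equation basic, and the trial's aim is preliminary efficacy. No extension is described, however, and the SAP still claims a 5% error rate and 80% power.

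**Conclusion.** The concern holds. For continuous outcomes with complete data, the classroom intercept has no influence on the tested interaction; with 15% attrition its influence is negligible. The test is anti-conservative whenever classes differ in change.

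Over classes of 12 to 27 and post-test ICCs of .01 to .10, type I error runs from 5.2% to 15.1% if only immediate-arm classes cluster and from 5.9% to 23.2% if both arms do. These ranges assume 216 analysed, r = .25 and class variance arising only after baseline. The direction is certain once class variance in change exceeds zero; the size cannot be fixed from the documents. This should be corrected before analysis, but it does not invalidate the design.

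**What to change.** 1. Add a classroom-by-time random effect (u_1j × Time) to the SAP equation, and keep it even if its estimated variance is near zero.
2. State whether waitlist students are grouped in their classes before the post-test. Limit the new term to the immediate arm only if they are not: in simulation the limited version reached about 10% when waitlist classes also clustered.
3. Use Kenward-Roger or Satterthwaite degrees of freedom for continuous outcomes. For binary outcomes use a t reference with between-class degrees of freedom, or a class-level analysis. A class-level t-test on mean change is a simple alternative throughout.
4. If a baseline-adjusted post-test model with a classroom effect is preferred, name it in advance. It is a different estimator, not an equivalent one.
5. In the power paragraph, state the number of classes and an assumed ICC, say whether that ICC refers to the post-test or to change, and restate power using the design effect in Step 2.
6. Correct the classroom index: the SAP defines j as classroom but writes the term as u_0i.

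The cost is SAP wording, one extra model term and a recorded class ID. Intervals will be wider, degrees of freedom fewer and stated power less favourable. With few classes, the class variance will be poorly estimated.

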To test the preliminary efficacy of the [REDACTED] Journey of Transformation–Native Youth Health Leadership Program (CHJ) which is an adapted and expanded version of the Discovering Our Story intervention curriculum, a 2010 SAMSHA-identified best practice AIAN strengths-based comprehensive substance use and health risk prevention and health leadership program for AIAN youth.

Outcomes:

- decrease rates of ATOD (marijuana and other drugs) use, intentions to use, susceptibility,
- increase refusal efficacy;
- decrease sexual activity (number of partners, condomless intercourse
- delay sexual initiation,
- increase sexual self-efficacy (i.e., refusal, avoidance), and safer sex intentions.

Examine how stressful life events, mental health (depression/anxiety/self-esteem), cultural protective (identity, enculturation, collectivist values, community connectedness, communal mastery, benevolence/traditionalism) and PYD-related factors (e.g., connectedness, efficacy, ATOD and sexual refusal) moderate or mediate the intervention's efficacy.

1.6 Study design. Provide a one-sentence description of the general study design and/or type of methodology.

Your answer will help HSD in assigning applications to reviewers and in managing workload. Examples: a longitudinal observational study; a double-blind, placebo-controlled randomized study; ethnographic interviews; web scraping from a convenience sample of blogs; medical record review; coordinating center for a multi-site study.

A randomized waitlist stepped wedge design with study participants recruited in staggered cohorts, with those in each annual recruitment wave receiving *individual-level random assignment* to either immediate intervention or waitlist control.

1.7 Intent. Check all the descriptors that apply to your activity. You must place an “X” in at least one box.

This question is essential for ensuring that your application is correctly reviewed. Please read each option carefully.

Descriptor
 1. Class project or other activity whose purpose is to provide an educational experience for the researcher (for example, to learn about the process or methods of doing research).
 2. Part of an institution, organization, or program’s own internal operational monitoring.
 3. Improve the quality of service provided by a specific institution, organization, or program.

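### Testing change with a free baseline arm difference, despite individual randomisation, costs about 1.1 to 1.6 times the variance of a shared-baseline model for continuous outcomes at the SAP's own r = .25

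*SAP*

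**What the plan says.** The SAP (Statistical Design and Power) fits one mixed model per outcome, with random intercepts for classroom and student. Its fixed part begins "b_0 + b_1 Intervention_i + b_2 Time + b_3", so the arms have separate baseline means (b1) and separate changes (b3). Only b3 is tested: "The statistical test of the CHJOT curriculum will be the Intervention by Time interaction". The SAP has no baseline covariate and no constraint of equal baseline means, and gives no reason for leaving b1 free. The power paragraph is built on the same interaction. It sets the pre-post correlation at r = .25, a level "of the outcome measures, which is reasonable given the short interval between assessments".

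Protocol 1.6 specifies "individual-level random assignment". Protocol 7.2 says of interested students that "they will be randomly assigned to a class offering the intervention sessions", some classes starting in the fall and others in the spring. Protocol 5.1 gives both arms a fall baseline. For the immediate arm: "Week 1. Take a 30-40 minute online baseline assessment". Of the waitlist group it says that "they will only take the baseline assessment in the Fall".

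**The concern.** Under individual randomisation the true baseline means are equal. A model that estimates b1 subtracts the whole observed baseline difference, noise included, from the follow-up difference. When baseline predicts follow-up weakly, that subtraction adds more noise than it removes, and r = .25 is low enough for this to happen. Part of the information in a survey already being collected is then lost in the test of every continuous primary outcome.

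**Working it through.** **Inputs.** From the SAP: r = .25, 255 recruited, 216 analysed, d = 0.20, Type I error 5%. Assumed, because not stated: 1:1 allocation, a two-sided test, ICC .02 to .10, classes of 15 to 25. Outcome variance is set to 1.

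**The SAP's sample size.** With the repeated-measures ANOVA convention f = d/2 and two time points, the noncentrality is N·f²·2/(1 − r). Power of 80% needs 297 students at d = 0.20 and 246 at d = 0.22, so 255 is not reproduced by either. The attrition step does reproduce: 216/0.85 = 254.1, rounded up to 255. The variance ratios for complete data below do not depend on N.

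**No classroom variance, complete data, N = 216.**
- Planned test (b1 free): Var(b3) = 8(1 − r)/N = 6/216 = 0.02778, SE 0.167 SD.
- Shared baseline (b1 = 0): Var(b3) = 4(1 − r²)/N = 3.75/216 = 0.01736, SE 0.132 SD.
- Ratio: 2(1 − r)/(1 − r²) = 2/(1 + r) = 1.60.

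Per participant the variances are 1.50 (raw change), 1.00 (baseline ignored) and 0.94 (shared baseline). Without classroom variance, raw change is less precise than discarding baseline altogether.

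**255 baselines and 216 follow-ups, all in the likelihood.** Planned: 4[(1 − r²)/216 + (1 − r)²/255] = 4[0.004340 + 0.002206] = 0.02618. Shared: 0.01736. Ratio 1.51.

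**With the SAP's time-constant classroom intercept.** This intercept cancels out of the change contrast, so the planned SE stays at 0.167. It does not cancel out of the shared-baseline estimator. For equal classes of size m, generalised least squares gives a ratio of 2/(1 + ρ), where ρ = [r + (m − 1)ICC]/[1 + (m − 1)ICC] is the pre-post correlation of class means. For example, ICC .02 and m = 15 give ρ = 0.53/1.28 = 0.414 and a ratio of 1.414.

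| Assumed ICC | m = 15 | m = 25 |
|---|---|---|
| .02 | 1.414 | 1.339 |
| .05 | 1.283 | 1.205 |
| .10 | 1.185 | 1.124 |

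The shared-baseline SE runs from 0.140 (ICC .02, m = 15) to 0.157 (ICC .10, m = 25). To match 216 students under the shared baseline, the planned test would need 216 × 1.124 = 243 to 216 × 1.414 = 306. With 255 baselines and classes of 20 the ratios are 1.32, 1.21 and 1.13 at ICC .02, .05 and .10.

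**Power at d = 0.20, n = 216.** The SAP does not say how d is scaled, so three readings are shown.

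| Reading of d | Effect in outcome SD | Planned | Shared, no clustering | Shared, ICC .02–.10 |
|---|---|---|---|---|
| Outcome SD | 0.20 | 22% | 33% | 25–30% |
| Change-score SD | 0.20 × √1.5 = 0.245 | 31% | 46% | 34–42% |
| f = d/2 | 0.40 | 67% | 86% | 72–81% |

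**A pooled-slope ANCOVA is not an equivalent remedy.** In a simulation of 12 classes of 18 (4,000 replicates), the ratio of the planned variance to that of an ANCOVA on the student's own baseline was 1.30, 1.08 and 0.77 at ICC .02, .05 and .10. At the highest ICC that ANCOVA is less precise than the planned test.

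**The case against.** The strongest reply is that nothing here is an error. The interaction test is valid, and it is the test the SAP powers. That is right, and it limits the point to efficiency.

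The figure of 1.60 needs zero classroom variance, although the SAP fits a classroom term, and r = .25 is only a planning value. Both points are fair. At r = .50 the ratio is 1.33 unclustered, 1.24 at ICC .02 in classes of 15, and 1.08 at ICC .10 in classes of 25. The gain shrinks but stays above 1 in each of these cases.

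The shared baseline also gives up some robustness. If the arms truly differed at baseline by b1 and the difference persisted, the planned test would be unaffected. The constrained estimate would shift by (1 − ρ)b1: 0.75·b1 without clustering, or 0.28·b1 at ICC .10 in classes of 18. An assumed true difference of 0.10 SD would then bias the estimate by up to 0.075 SD. Such a difference is possible. Assignment is made before classes start, students may change class, and the survey, the mentor meetings and the programme in which students "attend 16 health sessions related to healthy behaviors" all begin in Week 1. This objection stands as a condition on the fix.

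Allocation ratios that varied between annual waves could also break the pooled equality. The documents do not say that they vary, and a wave term would deal with it.

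Finally, read literally, Protocol 5.1 leaves the waitlist arm's fall post-test unclear. The planned b3 needs that measurement just as much, so this does not favour either model.

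**Conclusion.** The point holds, as an avoidable loss of precision and not a bias. For continuous outcomes at the SAP's r = .25, the planned test has about 1.1 to 1.6 times the variance of a shared-baseline mixed model. The upper end (1.60, or 1.51 with the planned attrition) assumes no classroom variance. The range of 1.41 to 1.12 rests on an ICC of .02 to .10 and classes of 15 to 25, which are assumptions. All figures assume 1:1 allocation and two time points. The size of the loss for the logit outcomes is not established. Absolute power depends on how d is scaled, but the shared baseline is ahead on each reading. The change should be made before outcome data are analysed, so that the choice is pre-specified.

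**What to change.** In the SAP:
- Keep the mixed model and its classroom term, code Time 0 at baseline and 1 at post-intervention, omit b1 so that both arms share one baseline mean, and test b3. The same constraint can be set in the logit models.
- Do not substitute an ANCOVA with a pooled slope on the student's own baseline.
- State that the Week 1 baseline survey comes before the first mentor meeting and the first session. If allocation ratios differ between annual waves, add a wave term.
- Keep the model with b1 free as a sensitivity analysis, and update the power paragraph to name the new primary test.

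The cost is wording: no new data, students or surveys. The change adds one assumption, that baseline answers are not affected by knowledge of arm or by early sessions. The stated order of Week 1 events and the sensitivity analysis are there to support and check it.
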